7.1 SOC Procedures

7.1.1 Cleaning the Index Ulcer

Remove all dressings and wash the foot. The leg should be elevated for as much time as possible during this process. Wash the foot with sterile water or saline solutions. Gently irrigate the index ulcer prior to each dressing change with the same solution. Wound cleansers containing antiseptics (examples: Hypochlorous Acid, Vashe, ExSept, Preplt, etc.) are prohibited for use during the duration of this study.

During the Treatment Phase, the washing and cleaning of the DFU must be done prior to application of SOC primary dressing

7.1.2 Debridement of the Index Ulcer

Debridement is an essential technique and SOC in the treatment of DFU. It is important to remove all non-viable and necrotic material from the index ulcer prior to enrolling the patient. Debridement is allowed during the treatment phase at the treating Investigator's discretion. For detailed guidelines please see Appendix E.

7.1.3 Offloading

Offloading is essential if the wound is to heal. A diabetic offloading CAM boot will be given to each subject or if the subject cannot be accommodated into a CAM boot, a TCC will be provided.

Subjects will be educated on the importance of using the device to offload their DFU and instructed on keeping dressings dry and to call or visit the study site if the dressing becomes soiled, wet or is removed. In addition, subjects should be educated on wound infection and if they observe infection, to call or visit the study site.

7.2 Concomitant Medications

The subject may be administered any necessary medications, at the discretion of the Investigator; provided such medications are not applied topically to the index ulcer surface (topical medication can be applied to other surfaces around the ulcer or other non-reference ulcers).

All medications and therapies administered or taken by the subject beginning 30 days prior to signing the ICF and throughout the study will be recorded in the source documents and for randomized subjects, on the appropriate CRF.

7.3 Prohibited Medications and Therapies

The following treatments and medications are prohibited 30-days prior to screening period and throughout the trial:

- Any cellular and/or tissue-based products or wound dressings that include growth factors (e.g., EpiFix, Regranex, Dermagraft, Apligraf, GraftJacket, OASIS, Primatrix, Matristem)
- Revascularization surgery on the lower extremity with the index ulcer

Confidential Page 39 of 73

Radiation therapy to the foot

Excluded at SVI

- Topical antibiotics* or other topical agents, including or containing silver, honey, hydrofera blue, etc. (with the exception of anesthetics used during debridement)
- Systemic steroids/oral corticosteroids in excess of 10mg daily dose. (Note: inhaled steroids are acceptable)
- Other immunosuppressive agents and chemotherapy
- Cytotoxic therapies
- Negative pressure wound therapies
- Hyperbaric oxygen
- Any other investigational treatment/medications in the Investigator's opinion are likely to seriously impact wound healing
- Heat lamps
- UV lights
- Whirlpool baths
- Water PiksTM
- Jet water streams (other than gentle water irrigation)
- Wound cleansers that contain active ingredients and are not just normal saline (e.g., Hypochlorous Acid, Vashe, ExSept, Preplt, etc.)
- Selective COX-2 inhibitors (such as Celecoxib)

7.4 Allowable Medications and Therapies

The following medications and therapies are allowed during the study, if in the opinion of the Investigator, they are required for proper care of the study subject:

- Use of anesthetics for debridement
- Treatment with systemic antibiotics for acute or chronic infection, however, prophylactic use of systemic antibiotics is not allowed
- Other medications/therapies that are not otherwise prohibited and in the opinion of the Investigator, are required for proper medical care

Confidential Page 40 of 73

^{*}Topical antibiotics must be stopped at the first screening visit.

7.5 Approved Dressings

The following is a list of approved dressings suitable for study DFUs receiving SOC treatment:

SOC FIBRACOL™ Group

- FIBRACOL™ Collagen / Calcium alginate
- Plain foam (e.g., Allevyn gentle, Mepilex)
- Three-layer dressing, (4x4 gauze, soft cast roll, ace bandage / coban)

SOC MIRRAGEN™ Group

- MIRRAGEN™ Wound Matrix
- Plain foam (e.g., Allevyn gentle, Mepilex)
- Three-layer dressing, (4x4 gauze, soft cast roll, ace bandage / coban)

Confidential Page 41 of 73

8 Description of Protocol Assessments and Procedures

8.1 Informed Consent

Written informed consent will be obtained for this study by the Investigator or suitably qualified designee from all subjects before the collection of any protected health information and performance of any protocol-specific procedure.

In obtaining and documenting informed consent, the Investigator must comply with applicable regulatory requirements and must adhere to Good Clinical Practice (GCP). The Investigator, or designee, must fully inform subjects of all pertinent aspects of the study. Before informed consent may be obtained, the Investigator, or a person designated by the Investigator, must provide the subject ample time and opportunity to inquire about details of the study and to decide whether or not to participate in the study. All questions about the study must be answered to the satisfaction of the subject. Prior to the subject's participation in the study, the ICF must be signed and personally dated by the subject and by the person who conducted the informed consent discussion. For screen failure subjects who rescreen at a later date, reconsenting is required.

8.2 Assessment of Eligibility

At each visit during the Screening Period, the Investigator must assess a subject's continued suitability and eligibility for the study, especially with regard to the Inclusion and Exclusion criteria. If the subject is no longer suitable or eligible for the study, the subject will be considered a screen failure. Screen failure subjects may be re-entered into the study at a later time and re-screened.

Further, a panel of three board-certified plastic surgeons will review each wound, as well as inclusion/exclusion criteria, in a blinded fashion to ensure that randomizations are appropriate. The review will occur between SV2 and the day of randomization. The plastic surgeon will provide correspondence to the trial manager that the subject is appropriate for randomization, prior to the site being able to randomize the patient.

8.3 Re-Screening

If a subject initially fails to meet Inclusion/Exclusion criteria and is later reconsidered for participation, the subject will be re-consented and assigned a new screening number at the time of re-screening. Subjects who fail their first screening attempt may be re-screened again (i.e., up to two screenings) and may be enrolled if they are found to meet all Inclusion and none of the Exclusion criteria at the second screening visit.

8.4 Subject Demographics, Medical History and Ulcer History

8.4.1 Demographics

For the purposes of this study, demographic information will include:

- Date of ICF signature
- Date of birth
- Gender
- Race (American Indian/Alaskan Native, Asian, Black/African American, Native Hawaiian/Pacific Islander, Caucasian or other)
- Ethnicity (Hispanic/Latino or Not Hispanic/Latino)

Confidential Page 42 of 73

Use of tobacco products

8.4.2 Medical History

A medical history will be recorded during the Screening Period and will include:

- All ongoing medical conditions
- All previously resolved medical conditions related to diabetes or foot ulceration or which are relevant in the opinion of the Investigator

Events that emerge prior to the randomization visit will be recorded in the medical history and not as Adverse Events. Aside from being used to determine subject eligibility, this information will permit the Investigator to record the nature, duration and severity of any ongoing baseline medical conditions that occur prior to randomization

Medical histories will be recorded using the body system categories outlined below:

Cardiovascular

Respiratory

Gastrointestinal

Renal

Hepatic

Neurological

Endocrine

Lymphatic

Hematologic

Immunologic

Dermatologic

Psychiatric

Genitourinary

Other

DFU History

For each relevant history, the following will be documented:

- Disease/disorder/condition
- Date of diagnosis
- History status (resolved or ongoing)

8.4.3 Foot Ulcer History

Duration of the current DFU

Note: "Duration" is defined as the length of time that the index ulcer has been open at this location since the last time it was fully closed.

- Current offloading system used for the DFU (if any) and length of time that this has been used
- Prior treatments that have been used on the DFU for up to 1-year
- Age when the subject developed his/her first DFU
- Total number of previous DFUs
- Location of the current DFU

Note: "Index ulcer location" is defined by the ulcer being on the left or right foot, by the location of the ulcer on the foot, dorsal or plantar, toe (which toe), forefoot, midfoot, hind foot, ankle heel and by the positioning of the ulcer as lateral, medial, dorsal, or plantar located.

- Number of additional DFUs and location of each present at the screening visits
- History of DFU recurrence

Confidential Page 43 of 73

Note: "Recurrence" is defined as the re-opening of the index ulcer after complete healing.

- History of any amputations in the study foot and contralateral foot or leg
- History of any significant foot deformities, dermatological abnormalities, fungal lesions, or other findings.

8.4.4 Physical Exam

The physical examination will include routine examinations for the following:

- Head, ears, eyes, nose, and throat
- Abnormalities of the extremities
- Neurologic abnormalities
- Heart/cardiovascular abnormalities
- Musculoskeletal abnormalities
- Dermatologic abnormalities
- Any other body system for which an abnormality is noted and which, in the opinion of the Investigator, is relevant to the safety of the subject or could impact safety or efficacy results for the subject, i.e., the abnormality is clinically significant

Each abnormality will be recorded, and the Investigator will record an assessment of its clinical significance.

8.4.5 Vital Signs

The following vital signs will be collected:

- Height
- Weight
- Body mass index (BMI)
- Seated blood pressure (take after the subject has been seated for at least 5 minutes)
- Pulse
- Temperature

8.4.6 Pregnancy test

Females who are of childbearing potential must have a urine or blood pregnancy test at SV1 and at TV6.

8.5 ABI or Arterial Doppler Ultrasound

ABI, also known as the Winsor Index and the Ankle Brachial Pressure Index, is the ratio of blood pressure measured at the ankle to that measured at the arm. Details of the procedure can be found in Appendix B. An ABI < 0.8 indicates that there is a high probability that arterial insufficiency is present (positive predictive value 95% in a general practice population).

It should be noted that incompressible, calcified arteries may occur in diabetes causing a falsely elevated ABI, so if the subject has other signs or symptoms that could suggest peripheral arterial disease, further investigations to determine vascular status may be warranted.

Confidential Page 44 of 73

A documented record of an ABI test performed using the index ulcer leg, within one month of SV1 is acceptable for the purposes of this study, otherwise this must be completed in the Screening Period.

As an alternative arterial Doppler ultrasound can be performed evaluating for biphasic dorsalis pedis and posterior tibial vessels at the level of the ankle.

8.6 SPP

SPP provides another noninvasive method for measuring microcirculatory pressure of the artery at the skin level. It measures the pressure at which perfusion first returns to the cutaneous microcirculation following a controlled release of occlusion. SPP is useful in assessing the ischemic severity of lower limb and predicting ulcer healing in chronic critical limb ischemia with a value of <30 mmHg. See Appendix C for the appropriate technique of assessment.

8.7 **TCOM**

A TCOM assesses the partial pressure of oxygen molecules dissolved in the blood plasma. The amount of oxygen detected by the sensor is a balance of the oxygen delivery and local physiologic demands and reflects the metabolic status of the skin; it indicates the level of oxygen available at the ulcer site to assist in the ulcer healing process. A TCOM less than 30 mmHg of oxygen indicates impaired ulcer healing and ischemic disease. An appropriate technique for a TCOM assessment is provided in Appendix D.

8.8 WOUND-Q Assessment

The WOUND-Q will be administered to all subjects on SV1, TV3, TV7 and EOS1. This tool will document the impact of the wound on the subject's life and whether the treatment interventions helped to return them to improved functioning.

If a subject discontinues the study, every effort should be made to contact them to complete the WOUND-Q tool on their EOS1 visit.

Further details and the tool itself can be found in Appendix E.

8.9 Pain Assessment: NPRS

Pain intensity of the reference DFU is to be assessed before any dressing changes or other ulcer manipulations at all screening and treatment visits.

The subject will be asked to indicate a numerical value that best represents the current pain intensity at the index ulcer site on a scale of 0 to 10, anchored by word descriptors at each end, as "no pain" on the left side and "worst possible pain" on the right side of the number line. The number 0 represents "no pain," the number 5 represents "moderate pain", and the number 10 represents the "worst possible pain." The subject indicates the level of pain intensity by selecting a number on the line shown in Figure 3 below that represents their perception of their current state.

[figure not shown]

FIGURE 3: SUBJECT PAIN SCALE (NPRS)

Confidential Page 45 of 73

8.10 Ulcer Assessments

A number of different index ulcer assessments are required, including appearance, exudate characteristics, infection, and peri-wound characteristics.

8.10.1 Index Ulcer Appearance Assessment (Pre-debridement)

Index Ulcer Appearance Assessment (pre-debridement) categories includes:

- % Granulating (red/brown bumpy tissue that bleeds upon light debridement)
- % Non-viable tissue
- % Epithelialized Skin

Note: the categories should add to 100%.

8.10.2 Index Ulcer Exudate Assessments

The Investigator will determine the amount and type, if any, of index ulcer exudate. In determining the amount of index ulcer exudate, the Investigator must take into account the amount of exudate absorbed into the index ulcer dressing. Table 2 below details the categories will be used to quantify the amount and describe the type of index ulcer exudate:

TABLE 2: INDEX ULCER EXUDATE ASSESSMENT

Index Ulcer Exudate Assessment					
Volume	No exudate				
	Minimal amount				
	Light (scant) or small amount				
	Moderate amount				
	Heavy/large/copious amounts				
Туре	Not applicable: no exudate present				
	Serous: clear or light-yellow watery plasma				
	Serosanguinous: pink to light-red watery plasma				
	Sanguineous: red with fresh bleeding				
	• Purulent: thick and opaque exudate, of creamy yellow, green, white,				
	or tan color				

8.10.3 Index Ulcer Infection Assessments

The presence/absence of the following signs of infection at the index ulcer site will be documented at each visit. Infection of the index ulcer will be assessed using the STONEES method developed by Woo and Sibbald.¹⁹ Table 3 below lists the criteria for considering an index ulcer infected:

TABLE 3: INDEX ULCER INFECTION ASSESSMENT

Index Ulcer Infection Assessment Three or more of the following signs or symptoms are present: Increased surface area Increased peri-wound margin temperature by more than 3°F difference between two mirror image sites Exposed bone or can be probed to the bone

Confidential Page 46 of 73

- New areas of breakdown or satellite lesions
- Presence of swelling or reddened skin in peri-wound area
- Increased wound drainage
- Unpleasant, sweet, or sickening odor present

NOTE: An ulcer that Is deemed to be infected with three or more of the following signs will undergo a wound culture to confirm the presence of infection and identify the pathogenic organism, so the study subject receives the most appropriate antibiotic treatment

Infection at Index Ulcer site prior to Randomization

If the infection occurs prior to randomization i.e., prior to TV1, then the subject will be ineligible to be randomized.

Infection at Index Ulcer site after Randomization

If infection of the index ulcer site occurs after randomization *i.e.*, after the Randomization visit, record the infection as an adverse event and treat it as appropriate with oral antibiotics at the discretion of the Investigator.

Note: application of topical antibiotics and anti-microbial dressings to the index ulcer site are prohibited.

A subject with an infected index ulcer that is being treated by the Investigator will remain in the study unless the situation requires an alternative methodology that violates the protocol. Antibiotic interventions will be recorded on the Concomitant Medications CRF, and the event will be categorized as an Adverse Event, serious if it meets the definition of that category. All subjects who show evidence of an ulcer infection must have it reported on an Adverse Event CRF.

All subjects will be instructed to contact the Investigator if signs or symptoms of infection develop prior to their next scheduled visit.

During an episode of infection, the Investigator should not continue TCC, if it is being used, until the infection is resolved, and dressings should be changed at least every 72 hours.

Evaluate the skin surrounding the index ulcer for presence of signs such as erythema, edema, and cellulitis.

8.10.4 Investigator Assessment of Index Ulcer Closure

"Complete healing" of the index ulcer is defined as 100% re-epithelialization without drainage. At each visit, the Investigator will assess the ulcer by answering the following questions:

- Index ulcer 100% re-epithelialized?
- Drainage is absent?

Both questions must be answered "yes" for the index ulcer to be considering having reached "complete closure."

The date of complete healing is defined as the date of the first assessment of 100% reepithelialization.

Confirmation of Wound Healing

Confidential Page 47 of 73

Note that if a wound is initially judged as healed, it must be confirmed as healed with one healing confirmation visit at two weeks (plus or minus three days, HCV 1). The assessment details can be found in section 4.3.2.

Index Ulcer Photographs and Measurements

The index ulcer will be digitally imaged with a Sony digital camera that is at least 20 (twenty) megapixels, with the photo taken at a focal distance of 18 inches and a two-dimensional calibration scale. The Investigator will also take a planimetry photo for appropriate wound measurement.

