4.5.3.2 TV1: Randomization

The following assessments and activities are performed at this visit:

- Randomize the subject
- Apply appropriate treatment to index ulcer:
 - Apply SOC therapy with MIRRAGEN™ group 1
 - Apply SOC therapy with FIBRACOL™ group 2
- Apply outer layer dressing
- Ensure offloading of the wound is satisfactory
- Schedule the next study visit for one week later (±3 days)

4.5.3.3 Treatment Phase Visits: Weeks 2-12 (with additional tests week 2, 3, 4, 6 and 7 listed below)

The following assessments and activities are performed at these visits:

- Medical history changes from previous visit
- Physical examination changes from previous visit
- Assess concomitant medications, changes from previous visit and prohibited therapies
- Vital Signs

Confidential Page 28 of 73

- Pain assessment (see section 8.9)
- Assess Blood glucose
- Assessment of offloading
- Index ulcer foot neuropathy Semmes Weinstein 10-point test with vibratory; See section 8.14
- Check for any changes in the subject's health and assess them for any adverse effects and adverse events
- Index ulcer closure assessment will be determined by a site Investigator
 - If the index ulcer is 100% re-epithelialized, the subject will be scheduled for an HCV two weeks later. Please perform all applicable assessments and study procedures.
- Index ulcer Assessments
- Check for signs of clinical infection. If a clinical diagnosis of infection has been made, then
 the subject can be treated with oral antibiotics, but topical antibiotics or antimicrobial
 dressings CANNOT be used on the study ulcer
- Clean the index ulcer
- Debridement of the index ulcer if applicable (see Appendix E)
- Digital imaging of the index ulcer
- Record Index ulcer measurements
- Apply appropriate treatment to index ulcer:
 - Apply SOC therapy with MIRRAGEN™ group 1
 - Apply SOC therapy with FIBRACOL™ group 2
- Ensure offloading of the index ulcer is satisfactory
- Apply outer layer dressing
- The next visit will be scheduled for one week (+/- 3 days)

4.5.3.3.1 TV2: Treatment Visit 2

In addition to the procedures required at every treatment visit, perform the following additional procedures:

SnapshotNIR (at select sites)

4.5.3.3.1 TV3: Treatment Visit 3

In addition to the procedures required at every treatment visit, perform the following additional procedures:

WOUND-Q

4.5.3.3.1 TV4: Treatment Visit 4

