4.5.4 End of Study (EOS1) Visit

The following assessments and activities are performed at this visit:

- Medical history changes from previous visit
- Physical examination changes from previous visit
- Assess concomitant medications, changes from previous visit and prohibited therapies
- Vital Signs
- Pain assessment (see section 8.9)
- Assess Blood glucose
- HbA1c
- Assessment of offloading
 - Index ulcer foot neuropathy Semmes Weinstein 10-point test with vibratory; See section 8.14
- WOUND-Q
- Check for any changes in the subject's health and assess them for any adverse effects and adverse events
- Index ulcer closure assessment will be determined by a site Investigator
 - If the index ulcer is 100% re-epithelialized, the subject will be scheduled for a Healing Confirmation Visit (HCV) two weeks later. Please perform all applicable assessments and study procedures.
- Index Ulcer Assessments
- Check for signs of clinical infection. If a clinical diagnosis of infection has been made, then
 the subject can be treated with oral antibiotics, but topical antibiotics or antimicrobial
 dressings CANNOT be used on the study ulcer

Confidential Page 30 of 73

- Clean the index ulcer
- Debridement of the index ulcer if applicable (see Appendix E)
- Digital imaging of the index ulcer
- Record Index ulcer measurements
- Ensure offloading of the index ulcer is satisfactory and make an appointment for the subject with their desired clinician for follow-up care OR if subject is healed apply outer layer dressing and schedule Healing Confirmation Visit two weeks later (+/- 3 days)
- SnapshotNIR (at select sites)
- Apply outer layer dressing

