4.5.5 HCV: Healing Confirmation Visit

Perform the following procedures and assessments at this visit:

- Medial History Changes from previous visit
- Physical examination changes from previous visit
- Assess concomitant medications, changes from previous visit and prohibited therapies
- Vital signs
- Pain assessment (see section 8.9)
- Assess Blood glucose
- Assessment of offloading
- Index ulcer foot neuropathy Semmes Weinstein 10-point test with vibratory; See section 8.14
- Check for any changes in the subject's health and assess them for any adverse effects and adverse events
- If wound has re-opened, clean index ulcer
- If wound has re-opened, apply outer layer dressing
- Debridement of the index ulcer if applicable (see Appendix E)
- Digital imaging of the index ulcer
- If wound has re-opened, index ulcer measurements
- Confirm that the wound remained completely epithelized
- If wound has re-opened, document any other index ulcer assessments. If this is the EOS
 visit, discharge the subject from the study and make an appointment for the subject with
 their desired clinician for follow-up care; otherwise continue subject in study with allocated
 treatment schedule

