9.1 Data Analysis

This study consists of primary, secondary and exploratory/tertiary (research) endpoints. Data analysis of study endpoints includes use of validated DFU wound healing measures, quantitative and qualitative analyses, as well as exploratory methodologies. Table 4 below details each study endpoint, corresponding data, and planned analyses.

TABLE 4: ETS WOUND CARE, LLC DFU ENDPOINT DATA ANALYSIS

Endpoint	Endpoint Description	Supporting Study Data	Endpoint Analysis
Primary	Comparison of the proportion of index ulcers "healed" at 12 weeks	Investigator assessment of healing (100% epithelization w/no drainage), measurements of ulcer size using digital imaging and photos	Adjudication panel will determine using photographs of the DFU
	Proportion of Index Ulcers healed at 6 weeks		
	PAR at 6 and 12 weeks	Digital imaging	Mathematical wound area change
	Time to healing within 6 and 12 weeks	Primary endpoint	Mathematical time based on healing
Secondary	Changes in peripheral neuropathy	Semmes Weinstein with vibratory	Mathematical change in scores
	Changes in wound quality of life	WOUND-Q (Quality of life tool)	Mathematical change in scores
	Change in pain levels during trial	NPRS	Mathematical change in scores
	Difference in cellulitis and/or infection at 12 weeks	Observation	Count of positive and negative responses
Exploratory/Tertiary	Changes in tissue perfusion of wound bed and periphery with treatment	SnapshotNIR	Exploratory

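### Section 8.10.4 dates healing by re-epithelialization alone, so some closure times for the secondary time-to-closure endpoint would be too early

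*Combined protocol and SAP*

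**What the plan says.** Section 8.10.4 has a two-part definition: complete healing "of the index ulcer is defined as 100% re-epithelialization without drainage". It puts two questions to the Investigator at each visit, one on re-epithelialization and one on drainage, and adds: "Both questions must be answered 'yes' for the index ulcer to be considering having reached" complete closure. The date rule in the same section has one part: "The date of complete healing is defined as the date of the first assessment of 100% reepithelialization".

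The visit instructions also have one part. For the weekly visits (Section 4.5.3.3): "If the index ulcer is 100% re-epithelialized, the subject will be scheduled for an HCV two weeks later". For end of study (Section 4.5.4): "If the index ulcer is 100% re-epithelialized, the subject will be scheduled for a Healing Confirmation Visit (HCV) two weeks later". At the HCV itself (Section 4.5.5): "Confirm that the wound remained completely epithelized".

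Other places point to two parts. Table 4 in Section 9.1 bases the primary endpoint on "Investigator assessment of healing (100% epithelization w/no drainage". Footnote [C] of the visit schedule describes the HCV step as confirming closure of the wound. Section 8.10.4 itself sends to the HCV a wound considered healed: "Note that if a wound is initially judged as healed, it must be confirmed as healed with one healing confirmation visit at two weeks".

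If the wound has reopened at the HCV, Section 4.5.5 keeps the subject on allocated treatment unless that visit is the end-of-study visit. No section says what then happens to the healing date. Time to closure is the first-listed secondary endpoint in Section 3. Section 9.2 analyses it by Kaplan-Meier within 6 and 12 weeks.

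**The concern.** The event and its date are defined by different criteria. A subject can be given a healing date at a visit where, by the protocol's own definition, the ulcer was not healed.

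The word *first* creates a second problem. Section 5.2 counts a success only if healing is confirmed two weeks later, and Section 4.5.5 foresees subjects who fail confirmation and go on. If such a subject closes later, the only dating rule in the protocol points back to the closure that failed.

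At stake is the event time for a named secondary endpoint that falls under the all-endpoint Hochberg procedure. In an open-label trial, sites and analysts could also apply different rules to the same wound.

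**Working it through.** **1. The plan's own figure.** The documents give no power, event count or expected time for time to closure. The only related figure is the power for the primary endpoint in Section 9.2: 120 per arm, 0.70 v 0.35, two-sided alpha 0.049, pooled Z-test, stated as 100%. With mean proportion 0.525:

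(0.35 × √120 − 1.969 × √(2 × 0.525 × 0.475)) / √(0.70 × 0.30 + 0.35 × 0.65) = (3.834 − 1.391) / 0.661 = 3.69, so power is 0.9999.

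The figure reproduces and does not depend on the date rule.

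**2. Criteria side by side.**

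| Step | Section | Criterion named |
|---|---|---|
| Definition of closure | 8.10.4 | epithelialized and no drainage |
| Primary endpoint data | 9.1, Table 4 | epithelialized and no drainage |
| HCV step in schedule | Table 1, footnote [C] | wound closure (two parts under 8.10.4) |
| Date of healing | 8.10.4 | epithelialized only |
| HCV trigger | 4.5.3.3, 4.5.4 | epithelialized only |
| HCV checklist | 4.5.5 | epithelialized only |

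Table 1 also leaves the ulcer assessments row, which under Section 8.10 includes exudate, blank at HCV1.

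**3. Shift per affected subject.** This assumes weekly visits continue until the ulcer meets the definition.

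- Draining at first full epithelialization, dry at the next visit: 7 days. With ±3 days on both visits the range is 7 − 6 = 1 to 7 + 6 = 13 days.
- Reopened at HCV, closed again at the next weekly visit at the earliest: 14 + 7 = 21 days nominal minimum.

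**4. Mean shift among healers.** Let f be the share with one draining visit and r the share that reopen and reclose; both are assumed. Mean days early = 7f + 21r.

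- f = r = 0.05: 0.35 + 1.05 = 1.4 days
- f = r = 0.10: 0.70 + 2.10 = 2.8 days
- f = r = 0.20: 1.40 + 4.20 = 5.6 days

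**5. Effect on the comparison (illustrative simulation).** Inputs: 20,000 subjects per arm; exponential healing giving 70% and 35% at week 12, so weekly hazards −ln(0.30)/12 = 0.100 and −ln(0.65)/12 = 0.036; times rounded up to weekly visits; a lag of 1 week for drainage or 3 weeks for reopening; censoring at week 12; Cox model. Each cell shows the first-epithelialization date v the date closure is actually met. M is MIRRAGEN and C is control.

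| Assumed share with each problem | Hazard ratio | Closed by week 12, M | Closed by week 12, C | Mean weeks to 12, M | Mean weeks to 12, C |
|---|---|---|---|---|---|
| 10% M, 10% C | 2.762 v 2.753 | 0.704 v 0.690 | 0.358 v 0.348 | 7.28 v 7.54 | 9.90 v 10.02 |
| 20% M, 20% C | 2.745 v 2.736 | 0.695 v 0.670 | 0.352 v 0.333 | 7.36 v 7.84 | 9.92 v 10.15 |
| 20% M, 10% C | 2.796 v 2.660 | 0.697 v 0.670 | 0.348 v 0.338 | 7.37 v 7.87 | 9.96 v 10.08 |
| 10% M, 20% C | 2.784 v 2.878 | 0.700 v 0.686 | 0.350 v 0.333 | 7.34 v 7.59 | 9.91 v 10.14 |

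The first-date hazard ratios differ between rows only by simulation noise, so the contrast within a row is what counts. With equal rates it is negligible. With unequal rates it goes either way. At 20% in both arms the restricted mean is 7.84 − 7.36 = 0.48 week too short for MIRRAGEN and 10.15 − 9.92 = 0.23 week for control. The arm with more closures has more dates shifted, so the absolute gap reads 9.92 − 7.36 = 2.56 weeks rather than 10.15 − 7.84 = 2.31. Restricted mean is used here only to summarize the curve; the plan does not name it as an analysis.

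**The case against.** Much of the plan points to the intended reading. Section 8.10.4 asks both questions at each visit without exempting the HCV. Table 4 derives time to healing from the primary endpoint, which excludes draining ulcers. Section 4.3.2 gives final confirmation to the adjudicators. The formal SAP is still to be written and could settle the date. All of this stands, and it makes the trigger and checklist wording a conflict between sections rather than a plain omission of drainage. It does not cure the date sentence, which contradicts the definition just above it.

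A reader might infer three stronger things that the documents do not support.

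- *The plan rules that a reopened ulcer keeps its first date.* It does not say so. That is the literal result of *first assessment*; the documents are silent on redating, and the sections on confirmation fit the other reading.
- *Draining ulcers will be counted as primary successes.* That needs the one checklist line in Section 4.5.5 to override the two-part definition, Table 4 and adjudication. Photographs may miss exudate absorbed into a dressing, so the safeguard is imperfect, but the harm is not established.
- *The rule favours MIRRAGEN.* At the planning rates there are 0.70 × 120 = 84 closures against 0.35 × 120 = 42, so an equal share of affected healers is twice as many subjects in the MIRRAGEN arm. That only restates the planned rates and leaves the hazard ratio almost unchanged.

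It is also unclear how many reopened subjects would continue. Section 4.5 brings the end-of-study visit forward when a wound heals, and Section 4.5.5 discharges a reopened subject at that visit.

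**Conclusion.** The point holds for the date rule. Taken as written, it gives too early an event time to ulcers still draining at first full epithelialization (nominally 7 days per such visit) and to ulcers that fail their HCV and close later (nominally at least 21 days). Dates for all other subjects are right.

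The frequency of either event cannot be derived from the documents. The range of 1.4 to 5.6 days among healers rests on assumed shares of 5% to 20% each and on the minimum lags. No bias in the treatment comparison, measured by the hazard ratio, is shown when the rates are equal between arms. The effect is mainly on absolute closure times and Kaplan-Meier estimates for the secondary endpoint. The HCV trigger and checklist are a wording conflict to be reconciled. The change should be made, but it does not threaten the primary analysis.

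**What to change.** In Section 8.10.4, define the event date as the first visit at which both closure questions are answered yes and whose closure is confirmed at its own HCV. State that a closure failing its HCV is not an event and that follow-up time continues. Carry the same definition into the SAP before database lock.

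Reconcile Sections 4.5.3.3, 4.5.4 and 4.5.5 with Section 8.10.4, Table 4 and footnote [C], so that date, trigger and confirmation use one two-part criterion. Make sure that the drainage answer is recorded at the HCV.

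The cost is a few sentences and, if the case report form lacks it, one form item. The downside is that a few closures will be dated later or not confirmed.
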